This research will be done in three phases involving young adults, ages 18-34, susceptible to WTS (i.e., nonusers who do not oppose trying WTS)²⁷ or engage in WTS at least monthly. Phase 1 concerns selecting text and graphic health warnings that can strongly influence beliefs and feelings about personal risk and intention to quit or try WTS. We will create, refine, and select text and graphic health warnings in four domains: 1) longer-term health effects, 2) shorter-term health effects, 3) addictiveness, and 4) types and levels of toxicant exposures. We will also select the most appealing waterpipe product and social allure ads themes that entice young adults to engage in WTS. The top two text and graphic health warnings in each domain and the top two product and social allure ads within each theme will be used for Phase 2. In Phase 2, using the online consumer crowdsourcing platform Turkprime²⁸, susceptible nonsmokers and smokers (N=1000 per group) will be randomized to review ads with: 1) no health warnings, 2) text only health warnings, or 3) text + graphic health warnings. Nested within Arms 2 and 3 is health warning domain and ad theme. Reactions to ads will include ability to grab attention, cognitive and affective beliefs and attitudes toward each ad and ad appeal to engage in WTS. Main outcomes will include perceived risk and worry about harms (i.e., risk appraisal), attitudes

toward WTS, and intention to try or quit WTS. At a two-week follow-up, we will reassess these main outcomes, WTS, and recall of ad content. In Phase 3, using a new sample of susceptible nonsmokers and waterpipe tobacco smokers (N=100 per group), we will conduct an eye-tracking laboratory study to examine whether warnings evoke changes in attention that mediate changes in risk attitudes. The *primary aims* are to:

AIM 1 (Phase 1): Develop, pilot test, and select text and graphic health warnings in four domains (i.e., long/short-term health effects, addiction, type and level of toxicant exposures) that most dissuade WTS as well as select waterpipe tobacco product ads (themes of flavored tobacco, waterpipe apparatus) and social allure ads (four themes of eroticism, exoticism, social acceptance, and occasion appropriate) that most entice WTS.

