theme selected by each panel. Ads will be counterbalanced in a Latin-square design. For waterpipe product ads, participants will be randomized to review either the four tobacco- or four waterpipe apparatus-themed ads counterbalanced in a Latin-square design. Reactions to the social allure and waterpipe product ads will mirror those of the warnings. These will include: extent ad grabbed attention⁹⁶, credibility, relevance, fear appeal, extent ad influenced cognitive and affective beliefs about WTS¹⁰⁰, global attitude about ad⁹⁹, effort reviewing the ad, and extent ad *enticed* them to want to smoke (average of 2 items about ad making WTS more appealing and making them want to smoke 1=none at all, to 7=a great deal). They will rate extent each ad captured the social allure/product themes. Responses will be averaged for each ad within theme. *The top two ads within each social allure theme (8 total), and the top two within each product ad theme (4 total), with the highest mean score on enticing them to “want to smoke” waterpipe will be chosen for Phase 2.* All 24 ads will be used as stimuli for Phase 3.

Phase 2 Procedures:

Tests of ads with or without health warnings. Using Turkprime, we will recruit online 1000 waterpipe tobacco smokers and 1000 susceptible nonsmokers (\$2.00 payment). After screening and collecting baseline demographic and tobacco use data (e.g., cigarettes), participants will be stratified and randomized to review ads with or without health warnings. After obtaining participants' reactions to ads, we will assess key study constructs. All participants will complete a two-week follow-up.

Interventions. Participants will be stratified by sex and use of other tobacco products (no/yes) and then randomized in a 1:2:2 ratio to one of three arms: 1) no health warnings (i.e., review ads only – control); 2) text health warnings only; or 3) text + graphic health warnings. Nested within Arm 2 and 3 will be both ad themes (six total) and health warning domains (four total). Each arm is discussed below.

- *Control arm (N = 200).* Participants will be randomized with equal probability to one of the six ad themes (2 from product, 4 from social allure). They will view in counterbalanced order the two ads chosen for that theme from Phase 1 – no order effects are expected. They will not receive any warnings. (N ≈ 33 per cell).

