- *Text only health warnings (N = 400).* Ad theme selection will occur as with the control arm. Nested also as a between-subjects factor will be warning domain. Participants will see two text warnings from the same domain randomly assigned to the two ads within the same theme with ad order counterbalanced. Hence, this arm is primarily a 4 (warning domain: long-/short-term health effects, addiction, toxins) X 6 (ad theme: eroticism, exoticism, social acceptance, occasion appropriate, (flavored) tobacco, waterpipe apparatus) X 2 (ad order: A1A2 vs A2A1) between-subjects factorial design. Expecting no order effects, there are 24 main cells (N ≈ 32 per cell combining populations).
- *Text plus graphic health warnings (N = 400).* This arm is procedurally identical to the text only arm. The exception is that the two graphic warnings would be randomly added to the text warning in the same domain; thus, graphs are matched to the text warnings by health domain. (N ≈ 32 per cell combining populations).

Post intervention assessments. We will assess participants' reactions to each ad. *We will not assess reactions to warnings specifically; doing so may unduly bring attention to them.*

Reactions to warnings will have been obtained from Phase 1 and 3. After responding to the last ad, and aligned with the Message Impact Framework⁷², we will assess participants' knowledge of harms¹⁰², risk appraisals¹⁶, cognitive and affective beliefs and attitudes about WTS100, and intentions to quit/willingness to try WTS (4-item scale)¹⁴. We've used versions of these measures with $\alpha > .70$.

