We will use 90% power at .01 level of significance (two-tailed) for univariate tests and contrasts. Possible covariates obtained within the survey will include: race, sex, education, use of other tobacco products and among smokers, WTS frequency and level of addiction to WTS. Missing data will multiply imputed¹⁰⁵ as appropriate after checking missing randomness¹⁰⁶. For H2A and H2B, factorial MANOVAs will be conducted using SAS Proc GLM for all outcomes simultaneously. For H2A, if the omnibus multivariate test is significant at a .05 level, rather than .01, for the primary outcomes (risk appraisals, beliefs/feelings about WTS, global attitude about WTS, and intention to quit/willingness to try WTS), we will perform post-hoc univariate tests for each outcome at a .01 level for comparisons among: (a) ads without health warnings (control arm), with text warning only, and with both text + graphic health warnings; (b) four health warning domains; (c) six ad themes; d) two study populations; and interactions of a-d. Noteworthy, the interactions will be incomplete due to lack of health warnings in the control arm. Thus, Type IV sum of squares will be used to address empty cells. For H2B, the same statistical methods will be conducted as with H2A, using reactions to ads as the main outcomes. For H3, we have several mediators (reactions to ads). We will use the SAS Macro by Preacher and Hayes¹⁰⁷ to test multiple mediation effects in each study population. This approach address both multiple mediators simultaneously as well as multi-categorical variables¹⁰⁸ such as warning domains as proposed herein.

Importance / Value:

Waterpipe tobacco smoking (WTS) is becoming widespread in the United States among young adults^{17,18}. Increases in WTS are partly due to advertisements (ads) that entice young adults to engage in WTS^{19,20}. Often devoid of health warnings^{22,23}, waterpipe product and social allure ads likely mislead young adults to believe WTS is safe, promoting experimentation with WTS and reducing the desire to quit among users^{19,24}. Thus, as shown with cigarette health

warnings¹, designing effective text and graphic (i.e., pictorial) warnings is vital to curbing the effects of these ads.

Risks / Benefits:

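### The Phase 2 model is not written out, and if arm and warning domain are crossed, as the empty-cell remedy implies, the default arm test gives the control arm zero weight

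*Combined protocol and SAP*

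**What the plan says.** The design text treats domain as nested. Study Design states: "Nested within Arms 2 and 3 is health warning domain and ad theme". Phase 2 Procedures repeats it under Interventions ("Nested within Arm 2 and 3 will be both ad themes (six total) and health warning domains (four total") and again for the text-only arm ("Nested also as a between-subjects factor will be warning domain"). Control participants see no warning and so have no domain. They are, however, randomized to the same six ad themes, so theme is in fact crossed with arm.

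The section Sample Size (power calculations) and statistical considerations plans factorial MANOVAs in SAS PROC GLM. Univariate tests for H2A follow "if the omnibus multivariate test is significant at a .05 level, rather than .01, for the primary outcomes". They are run at .01 "for comparisons among: (a) ads without health warnings (control arm), with text warning only, and with both text + graphic health warnings", and also for "b) four health warning domains; (c) six ad themes; d) two study populations; and interactions of a-d". The interactions are then described as "incomplete due to lack of health warnings in the control arm. Thus, Type IV sum of squares will be used to address empty cells". Contrasts appear once, in general terms: "We will use 90% power at .01 level of significance (two-tailed) for univariate tests and contrasts". H2B is to use the same methods with reactions to ads as outcomes.

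The document gives no model statement, no domain code for control, no domain-within-arm term and no named contrast. Data Safety and Monitoring gives the primary goal as the effect of text warnings, text + graphic warnings, or no warnings.

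**The concern.** The only stated remedy for control having no domain is a type of sums of squares suited to empty cells. If domain is coded as nested in arm, no cell is empty and no remedy is needed. The remedy, together with the listed interactions of arm with domain, therefore points to a crossed model.

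In a crossed model control shares no domain level with either warning arm, and the default arm line cannot use control at all. It answers whether adding a graphic to a text warning matters. It does not answer whether warnings matter. Warnings that work about equally well in both formats could then be reported as showing no arm effect. If the multivariate gate is that same arm effect, the control comparisons might not be reached.

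**Working it through.** **1. The plan's own figures.** The stated total N of 3934, 657 and 289 (f = 0.10, 0.25, 0.40) reproduces from the noncentral F with λ = f²N, numerator df 2 × 3 × 5 × 1 = 30 (the four-way interaction), denominator df N − 144, alpha .01 and 90% power. The values of λ are 0.01 × 3934 = 39.34, 0.0625 × 657 = 41.06 and 0.16 × 289 = 46.24. These sample sizes are not in dispute.

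**2. Filled cells.** Control fills 6 themes × 2 populations = 12. The warning arms fill 2 × 4 domains × 6 × 2 = 96. The total is 108.

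**3. What the arm test can contain under crossed coding.** Give control its own domain level, none. Apart from theme and population, the cell means are:

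- control: μ + α(C) + δ(none)
- warning arm a, domain d: μ + α(a) + δ(d)

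δ(none) occurs only alongside α(C), so in any estimable function the two have the same coefficient. The arm hypothesis must put zero on every term that does not contain arm, including δ(none). Hence the coefficient of α(C) is zero. The other two must sum to zero, so the weights for (control, text, text + graphic) are (0, .707, −.707), with 1 df. Adding interactions changes nothing: the main-effects model (rank 12) and the model with all interactions (rank 108) give the same result. The restriction applies to Type III as well as Type IV.

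The df confirm it. For arm × domain, 9 filled cells give 8 model df, but arm 1 + domain 3 + interaction 3 = 7. The missing df is control versus warnings. In the full model the effects account for 95 of 107 df, and the missing 12 all involve control.

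If control's domain is left missing instead, PROC GLM drops those participants, so control is again absent.

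**4. Alternatives.** With domain nested in arm, the domain term contains arm and need not have zero coefficients. Arm then has 2 df and includes control (main-effects model, rank 15). Omitting domain also gives 2 df (rank 9).

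**5. Size.** Phase 2 Procedures gives 200/400/400 per population, hence 400/800/800. Alpha is .01. The effects, in SD versus control, are assumptions; the document gives none.

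- Three-arm test (2 df): λ = Σ nᵢ(μᵢ − μ̄)². At 0.20/0.30, μ̄ = 0.4 × 0.20 + 0.4 × 0.30 = 0.20 and λ = 400 × 0.04 + 0 + 800 × 0.01 = 24.0.
- Crossed arm test (1 df): λ = d² × 800 × 800/1600 = 400d², where d is the difference between text + graphic and text. At 0.20/0.30, λ = 400 × 0.01 = 4.

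| Text / text + graphic | λ crossed | Power crossed | λ three-arm | Power three-arm |
|---|---|---|---|---|
| 0.25 / 0.25 | 0 | 1.0% | 20.0 | 94.2% |
| 0.20 / 0.25 | 1 | 5.8% | 17.2 | 89.4% |
| 0.20 / 0.30 | 4 | 28.2% | 24.0 | 97.7% |
| 0.20 / 0.35 | 9 | 66.3% | 33.2 | 99.8% |
| 0.20 / 0.40 | 16 | 92.2% | 44.8 | >99.9% |

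The first row is the plan's small effect: f² = 20/2000 = 0.01, so f = 0.10. With domain nested in arm, power is 97.7% at 0.20/0.30 and 94.2% at 0.25/0.25, so nothing is lost. In 5000 simulated trials with main-effects models, the crossed test rejected in 28.1% at 0.20/0.30 and 0.9% at 0.25/0.25; the model without domain rejected in 97.5% and 94.1%.

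**6. Recovery by contrast.** An explicit control-versus-text contrast (400 v 800) has 75.4% power at 0.20 SD and 93.4% at 0.25 SD. The information is in the data; the default arm line does not use it.

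**The case against.** The strongest reply is that the plan already puts control in the comparison. It lists all three arms, promises tests among them, mentions contrasts, and describes domain as nested. It nowhere says that the default arm line is the reported test. An analyst would also see 1 df for a three-level factor and could write a contrast. All of this stands. A reader might infer that the plan excludes control, or that control effects cannot be estimated; the documents support neither.

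The Type IV sentence speaks of incomplete interactions and does not offer Type IV as the means of comparing control with the warning arms. That weakens the inference to crossing without removing it, since the choice would affect every line of the model. The complete 3 × 4 × 6 × 2 layout used for power is no evidence of crossing either, because the plan introduces it as a conservative device. The document also refers to research-plan sections that are not supplied, and model details may sit there.

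What remains is that the one remedy written down presupposes crossing and then does not deliver the first listed comparison. A repair chosen after seeing an odd df would be made after the data are in, which prespecification is meant to avoid.

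**Conclusion.** The point holds in conditional form. That the model and contrasts are not written out is plain from the document. That arm and domain are crossed is the most natural reading of the empty-cell remedy and the listed interactions, but it is an inference. If it is right, the default arm test has 1 df and gives control zero weight. The cost depends on how far the two warning formats differ: from 98% down to 28% power at 0.20/0.30, little at 0.20/0.40 (92% against more than 99.9%), and at worst 1% against 94% with equal effects of 0.25. If domain is nested, there is no loss.

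Three stronger readings are tempting and not supported:

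- That Type IV sums of squares are at fault. The cause is the coding, and changing to Type III would leave the problem in place.
- That the multivariate gate would stay shut. The plan does not say which test the omnibus test is, so no gate probability can be given.
- That the plan's own predictions show how far the formats will differ. Its prediction favouring text + graphic concerns sustainability and recall at two weeks, not the immediate outcomes. Equal effects are a bound here, neither expected nor ruled out.

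**What to change.** Write out the model for H2A, and the same for H2B. In place of reliance on Type IV sums of squares, use a model that keeps control in the arm effect:

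- domain nested in arm, which gives a 2-df arm test; or
- arm (3) × theme (6) × population (2) on all 2000 participants, without domain.

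With either, prespecify three contrasts: control v text, control v text + graphic, and text v text + graphic. State that the .05 multivariate gate for the three-arm comparison is the 2-df arm effect from that model. Test domain and its interactions in the two warning arms only (format × domain × theme × population, N = 800 + 800 = 1600), where all 2 × 4 × 6 × 2 = 96 cells are filled by design.

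If nesting was always intended, one sentence saying so, the three contrasts and the gate suffice, and the Type IV sentence can go. The cost is one extra model, or a few named contrasts in one nested model. No participants or data are added.

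### The H3 mediation models do not specify the randomised ad theme, so if theme is left out the reaction-to-outcome path can be confounded by a factor the trial itself assigns

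*Combined protocol and SAP*

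**What the plan says.** Under Phase 2 Procedures, the control-arm description states: "Participants will be randomized with equal probability to one of the six ad themes". The text-only arm selects themes in the same way, and the text-plus-graphic arm follows the text-only procedure. Theme is therefore independent of arm by design.

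The section on sample size and statistical considerations treats theme differently across hypotheses:

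- **H2A** lists "c) six ad themes" as a factor for the WTS outcomes, with interactions.
- **H2B** applies the same methods to reactions to ads.
- **H3** names reactions to ads as the mediators and a published macro as the tool, "to test multiple mediation effects in each study population". It adds that the approach handles multi-categorical variables "such as warning domains as proposed herein". There is no model equation and no list of terms, and theme is not mentioned.

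The covariate sentence in the same section reads: "Possible covariates obtained within the survey will include: race, sex, education, use of other tobacco products and among smokers, WTS frequency", and goes on to level of addiction. Theme is not in it.

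**The concern.** Randomising the arm protects the path from warnings to reactions. It does not protect the path from reactions to outcomes, because reactions are observed after assignment and are not themselves randomised. Any variable that shifts both reactions and outcomes confounds that second path unless it is in the model.

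Ad theme is a candidate for such a variable. Aim 2 explores its influence on both sets of measures. Suppose some themes make an ad better liked and also make WTS look better through something the reaction items do not capture. Participants with favourable reactions would then tend to have favourable outcomes even if reactions drive nothing. Combined with a real effect of warnings on reactions, this would be reported as mediation. If the two theme patterns run in opposite directions, real mediation could be masked.

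Mediation by reactions is Aim 3. Unlike most mediator-outcome confounders, this one is assigned by the trial and known for every participant.

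**Working it through.** **1. The plan's own figures.** The power paragraph covers the H3 general linear models and uses a complete 3 × 4 × 6 × 2 design, which is 144 cells. With a noncentral F test, noncentrality f²N, numerator df 2 × 3 × 5 × 1 = 30, alpha .01 and power 90%, the required N is 3934, 657 and 289 for f = 0.10, 0.25 and 0.40. All three match the plan. The power basis therefore contains the six themes. It does not say what enters the H3 models, and it pools the two populations, whereas H3 is run within each.

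**2. Inputs for the bias check.**
- From the documents: N = 1000 per population, split 200/400/400; six equally likely themes independent of arm; two-sided .01 for univariate tests.
- Assumed, because the documents give none: the theme effects, the effect of warnings on reactions (same in both warning arms), a single mediator, and no true reaction-to-outcome effect. Mediation is declared when both paths are significant, as a stand-in for the macro's own test.

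**3. Bias in the reaction-to-outcome path.** Let theme explain a share R²M of reaction variance and R²Y of outcome variance within arm, and let ρ be the correlation between the two theme patterns. With theme left out, in SD units:

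bias = ρ × √(R²M × R²Y)

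The standard error is about 1/√1000 = 0.0316, so z = bias/0.0316, compared with 2.576.

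| R²M / R²Y | ρ | Bias | z | Path significant at .01 |
|---|---|---|---|---|
| 10% / 5% | 1 | √0.005 = 0.071 | 2.24 | 37% |
| 10% / 5% | 0.5 | 0.035 | 1.12 | 7% |
| 10% / 2% | 1 | √0.002 = 0.045 | 1.41 | 12% |
| 5% / 2% | 1 | √0.001 = 0.032 | 1.00 | 6% |
| 10% / 5% | 0 | 0 | 0 | 1% |

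Simulation agrees: about 36 to 37% in the first row, 11 to 12% in the third and 4 to 6% in the fourth. With theme indicators entered, the rate is about 1% throughout. With ρ = −1 the bias in the first row becomes −0.071.

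**4. From path to indirect effect.** False mediation also needs a significant arm-to-reaction path. One warning arm against control has standard error √(1/200 + 1/400) = 0.087 SD. For the first row of the table:

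- Shift of 0.5 SD: z = 0.5/0.087 = 5.8, power above 99%. False mediation is about 0.37 × 0.999 = 37%; simulations give about 35%.
- Shift of 0.2 SD: z = 2.3, power 39%. False mediation is about 0.37 × 0.39 = 14%; simulations give roughly 12 to 19%, depending on how the arm path is tested.
- No shift: 0.37 × 0.01 = 0.4%, which is under 1%.

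At a 0.5 SD shift the other rows of the table carry over almost unchanged.

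**5. The same check on the plan's effect-size scale.** If theme has the same pattern with size f on reactions and outcomes, and residual SD is 1, the bias is f²/(1 + f²): 0.01/1.01 = 0.010, 0.0625/1.0625 = 0.059 and 0.16/1.16 = 0.138 for f = 0.10, 0.25 and 0.40. With a 0.5 SD shift and testing at .05, false mediation was declared in 6.5%, 47% and 99% of 1500 simulated trials each, against 4 to 5% with theme adjusted. If the true path is 0.3 and f = 0.25, the indirect effect is estimated as 0.179 instead of 0.150. If theme acts on reactions only, there is no bias.

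**The case against.** A reader might infer that the plan excludes theme from H3. The documents do not support that. H3 has no equation, its mention of warning domain is only an example, and the power basis covering H3 includes six themes. The covariate sentence proves little either way: it is confined to possible covariates from the survey, and arm and domain are absent from it too. What stands is that theme is unspecified.

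A reader might also infer that theme differences alone produce mediation, or always inflate it. Neither holds. Theme is independent of arm and cannot bias the arm-to-reaction path, so without a warning effect on reactions the false-mediation rate stays under 1% at .01. The direction depends on the alignment of the two patterns.

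Nor does the plan predict theme effects. Aim 2 explores them, and testing a factor is not forecasting its size or ordering. The 10%/5% fully aligned setting is a worst case among those examined. H3 enters several reaction measures together, which may capture more of theme's influence than the single mediator simulated here. With small theme effects the harm is slight.

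Finally, Aim 3 is exploratory, and the main arm comparison in H2A already carries theme explicitly. These points limit the size and importance of the problem. They do not give an analyst any instruction to include theme in H3.

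**Conclusion.** The concern holds as a gap in specification. H3 does not name ad theme, although theme is randomised in every arm and analysed for both the mediators and the outcomes. If it is left out, the reaction-to-outcome path is biased to the extent that theme reaches outcomes outside the measured reactions in a pattern correlated with its effect on reactions.

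The size rests wholly on assumed effects. With a 0.5 SD shift in reactions, false mediation at .01 runs from about 35% in the worst case to about 7% at half alignment and 4 to 6% at 5%/2%. It is at the nominal level when the patterns are uncorrelated. The change is worth making because this source of bias is known and removable, not because large bias has been shown.

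**What to change.** Write out the H3 mediator and outcome equations. Enter five ad-theme indicators in both equations of every H3 model. In models restricted to the two warning arms, where domain is not the exposure, add three domain indicators as well. A theme-by-warning term could be a sensitivity analysis.

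The cost is a short addition to the analysis section and 5 to 8 degrees of freedom (five for theme, three for domain) out of about 1000 participants per population, or 800 in models limited to the warning arms. No new data are needed and no sample-size figure changes. If the investigators already intended to include theme, the addition simply records it in advance.
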